9 STATISTICAL CONSIDERATIONS

Additional details of the planned statistical analyses will be provided in a separate statistical analysis plan.

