9.1 STATISTICAL HYPOTHESES

The proposed analysis is primarily descriptive rather than inferential, as it designed to provide a general assessment of participant level behaviors in the context of a community testing intervention. An exploratory hypothesize is that positive at-home SARS-CoV-2 antigen test results will lead to altered self-reported social interactions and altered health behaviors compared to negative test results.

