9.4 STATISTICAL ANALYSES

9.4.1 GENERAL APPROACH

The approach to analysis will be primarily descriptive. Demographics, questionnaire data, and testing results will be reviewed and summarized using graphical techniques and summary statistics. Where applicable, exact method confidence intervals will be computed around point estimates. Trends over time will be evaluated graphically. The proportion of participants adhering to social distancing guidelines after a positive vs. negative test result will be compared using tests of proportion clustered by participants with various levels of intra-participant correlation. Stratified analyses by test or week number will also be performed. We will explore the associations between positive test results and critical behavioral measures using mixed modeling techniques to account for the participant and

household correlations. Analyses will be conducted using SAS (SAS Institute, Cary NC) and R with R Studio (R-project).

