9.4.2 ANALYSIS OF THE PRIMARY EFFICACY ENDPOINT(S)

Point estimates with 95% confidence intervals will be reported. The analysis will be done for applicable study populations as described above, and stratified by participant demographics of interest (e.g., age, gender). There will be a comparison of the proportion of participants that report adhering to social distancing guidelines after positive vs. negative test result.

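### The positive-versus-negative comparison of distancing is pooled over time, and no week-adjusted or date-adjusted estimate is named as the headline

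*Combined protocol and SAP*

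**What the plan says.** Section 9.4.1 describes three analyses that bear on the primary contrast.

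- **Pooled test.** Adherence proportions after a positive and after a negative result "will be compared using tests of proportion clustered by participants with various levels of intra-participant correlation". No time term is named.
- **Strata.** "Stratified analyses by test or week number will also be performed". The section does not say whether the strata are combined into one estimate, or whether the pooled or the stratified result is the one to report.
- **Mixed models.** "We will explore the associations between positive test results and critical behavioral measures using mixed modeling techniques to account for the participant and" household correlations. Only the correlation structure is given.

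On time itself, the section says "Trends over time will be evaluated graphically". Section 9.4.2 repeats the primary contrast ("There will be a comparison of the proportion of participants that report adhering to social distancing guidelines after positive vs. negative test result") and adds demographic strata only. Calendar date appears in no analysis. Section 9.1 sets the tone: "The proposed analysis is primarily descriptive rather than inferential", with the positive-versus-negative hypothesis labelled exploratory. Section 9 adds: "Additional details of the planned statistical analyses will be provided in a separate statistical analysis plan".

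Section 1.3 schedules the social-interaction survey at Baseline and Weeks 1, 3, 5, 13 and 21. Section 1.1 gives a 4-week active testing period and up to 4 weeks of screening, so study week need not coincide with calendar week.

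**The concern.** In a pandemic, distancing and local positivity can both change within weeks. If they do, positive and negative responses come from different mixes of weeks. A pooled contrast then credits part of the cohort-wide change in distancing to the test result. The sign depends on whether positivity rises or falls while distancing drifts, so the plan could show a response that does not exist or hide one that does.

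A participant random effect does not cure this. It moves weight towards contrasts between a person's own positive and negative surveys, and those are contrasts between different times.

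The bias also does not shrink as the cohort grows, and Section 5.5 allows up to 300,000 participants. If the pooled and per-week results then disagree, the plan names no adjusted estimate to settle the matter.

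**Working it through.** **The plan's own figure.** The plan gives no number for the positive-versus-negative contrast. Its only precision figures, in Section 9.2, are for single proportions. For N = 5,000 and 50%, 1.96 × √(0.25/5,000) = 1.386%. Multiplying by √(295,000/299,999), a finite-population correction for 300,000, gives 1.374%, against 1.37% in the table. Those figures reproduce, but they say nothing about bias in a comparison.

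**Inputs.** The survey weeks during or just after testing are 1, 3 and 5 (Section 1.3). An average adherence of 50% is the illustration in Section 9.2. Weekly adherence and positivity are not in the documents, so the values below are assumptions. Every case has equal numbers per week and no effect of the result in any week.

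**Pooled gap.** With adherence a and positivity q in week t, gap = Σqa/Σq − Σ(1−q)a/Σ(1−q).

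| Adherence % | Positivity % | After positive | After negative | Gap (points) |
|---|---|---|---|---|
| 60/50/40 | 4/2/1 | 380/7 = 54.29 | 14,620/293 = 49.90 | +4.39 |
| 60/50/40 | 1/2/4 | 320/7 = 45.71 | 14,680/293 = 50.10 | −4.39 |
| 55/50/45 | 4/2/1 | 365/7 = 52.14 | 14,635/293 = 49.95 | +2.19 |
| 55/50/45 | 3/2/1.5 | 332.5/6.5 = 51.15 | 14,667.5/293.5 = 49.97 | +1.18 |
| 52/50/48 | 4/2/1 | 356/7 = 50.86 | 14,644/293 = 49.98 | +0.88 |
| 60/50/40 | 2/2/2 | 50 | 50 | 0 |
| 50/50/50 | 4/2/1 | 50 | 50 | 0 |

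Within any single week the gap is zero by construction.

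**Mixed model without a week term.** Assume a linear model with exchangeable within-person correlation ρ = 0.5 over three surveys, results independent across weeks, and no household effect. Let k = ρ/(1+2ρ) = 0.25, let c be adherence minus its mean, and let S = Σq. The coefficient tends to

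Σqc / {S − k[Σq(1−q) + S²] − (1−3k)S²/3}.

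- First row: 0.3 / (0.07 − 0.25 × 0.0728 − 0.25 × 0.0049/3) = 0.3/0.0514 = +5.8 points.
- Third row: 0.15/0.0514 = +2.9 points.
- Fourth row: 0.075/0.0477 = +1.6 points.

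Setting k = 0 returns the pooled +4.39 in the first row. Simulation (400 to 600 replicates per cell) agrees, and adding week indicators brought the bias to about zero.

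**Calendar time within a week stratum.** Take two equal enrolment waves in the same study week, with adherence 70% and 50% and positivity 4% and 1%. Positives average (4×70 + 1×50)/5 = 66.0%. Negatives average (96×70 + 99×50)/195 = 59.8%. The gap is +6.2 points with no effect, and stratifying by week does not remove it.

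**What separate strata can show.** With positivity 4/2/1%, N = 1,000 gives 40/20/10 positives per week. The 95% half-width at 50% adherence, 1.96 × √(0.25/n), is 15/22/31 points. At N = 10,000 (400/200/100 positives) it is 4.9/6.9/9.8 points. At N = 300,000 (12,000/6,000/3,000) it is 0.9/1.3/1.8 points.

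**The case against.** Several tempting stronger readings are not supported by the documents.

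- **That the mixed models exclude time.** They do not say so. Section 9.4.1 lists no fixed effects, Section 9.2 anticipates multivariable modelling, and Section 9 defers detail. The fair description is that time is unspecified. This stands.
- **That the plan ignores survey week.** Stratification by test or week number is planned beside the primary test, and within-week comparison removes bias that follows study week. In a very large cohort those strata would be precise enough to expose a false pooled gap. This also stands, but only in part. At 1,000 to 10,000 participants, the range discussed in Section 9.2, single-week estimates are too wide to settle a gap of 2 to 4 points. Nothing says that the strata are combined or preferred, and they do not handle calendar date.
- **That drift runs over the whole 29 weeks.** That total includes up to 4 weeks of screening, and scheduled testing lasts 4 weeks. The relevant drift is mainly over Weeks 1 to 5.
- **That the primary analysis has a known inflated false-positive rate.** The plan sets no significance level or decision rule for this contrast, and no trends are given from which to compute a rate. The largest gap above needs a 20-point fall in adherence and a fourfold change in positivity within about four weeks. Milder assumptions give about 1 point.

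The descriptive label lowers the stakes but does not remove them. The contrast is part of the primary endpoint in Sections 1.1 and 3, and a test is attached to it.

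**Conclusion.** The point holds as a matter of analysis choice. The comparison in Section 9.4.1 is pooled over time. No week-adjusted summary is named as the headline, the models' time terms are unspecified, and calendar date is handled nowhere.

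If adherence and positivity both move, the pooled contrast is biased in either direction: about ±4.4 points under strong assumed trends, about 2 under moderate ones, and about 1 or less under mild ones. A participant random intercept without a week term gives somewhat larger values at an assumed correlation of 0.5. If either quantity is flat, there is no bias.

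All trends are assumptions, and the calendar-date part rests on one two-wave example. A reader might infer that the planned result is wrong, but the documents cannot show that. This is a low-cost improvement to an exploratory comparison.

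**What to change.** In Sections 9.4.1 and 9.4.2, or in the separate analysis plan:

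- Name a week-adjusted positive-versus-negative difference as the headline. Use either a participant-clustered model with categorical survey week or a common difference combined over week strata.
- Add survey week (categorical) and calendar date of the survey as fixed effects in the mixed models.
- Keep the pooled unadjusted comparison as descriptive and the per-week results as supportive.

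No new data are needed. Survey week is set by the schedule in Section 1.3, and the app audit trail described in Section 10.1.9.1 records when entries are made. The cost is a few lines of text and extra terms in models already planned. The downside is a slight loss of precision, because weeks with few positives contribute little to the adjusted estimate.

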9.4.2 ANALYSIS OF THE PRIMARY EFFICACY ENDPOINT(S)

Point estimates with 95% confidence intervals will be reported. The analysis will be done for applicable study populations as described above, and stratified by participant demographics of interest (e.g., age, gender). There will be a comparison of the proportion of participants that report adhering to social distancing guidelines after positive vs. negative test result.

9.4.3 ANALYSIS OF THE SECONDARY ENDPOINT(S)

- The first secondary objective is to assess change in self-reported behaviors before and following SARS CoV-2 at-home test result over the study period. This will be measured via Precaution Adoption Process Model Assessments of self-reported data on awareness of the issue, engagement, decisions to act, action, and maintenance. The proportion of respondents that decide to act on precautionary behaviors after a test result will be analyzed for the entire study cohort and stratified by participant demographics of interest (e.g., age, gender).
- The second secondary objective is to assess the impact of at-home testing regimen on self-reported healthcare utilization for SARS CoV-2 treatment. This will be measured via self-reported Emergency Department visits, hospitalizations, and ICU admission for SARS CoV-2 evaluation or treatment. The proportion of respondents that decide to act on precautionary behaviors after a test result will be analyzed for the entire study cohort and stratified by participant demographics of interest (e.g., age, gender).
- The third secondary objective is to assess knowledge of SARS CoV-2 prevention approaches over the study period. This will be measured via self-reported data on perceptions and prevention of risks of contracting SARS CoV-2 infection. The proportion of respondents that are knowledgeable of precautionary measures to prevent infection will be analyzed for the entire study cohort and stratified by participant demographics of interest (e.g., age, gender).
- The fourth secondary objective is to assess prevalence of positive test result for SARS CoV-2. This will be measured via self-reported results of self-administered SARS CoV-2 antigen test. The prevalence of positive test results will be analyzed with 95% confidence for the entire study cohort and stratified by participant demographics of interest (e.g., age, gender).

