3 OBJECTIVES AND ENDPOINTS

Objectives	Outcome Measures	Endpoint
Primary		
1. To assess self-reported social interactions following SARS CoV-2 at-home test result over the study period	Assessments: self-reported data on social distancing, quarantine, social connectedness, healthcare utilization, well-being	Proportion of respondents that report adhering to social distancing guidelines after a test result for the entire study cohort and stratified by participant demographics (e.g., sex) of interest; comparison of proportion adherent after positive vs. negative test result
Secondary		
2. To assess change in self-reported behaviors before and following SARS CoV-2 at-home test result over the study period	Assessments: self-reported data on awareness of the issue, engagement, decisions to act, action, and maintenance	Proportion of respondents that decide to act on precautionary behaviors after a test result for the entire study cohort and stratified by participant demographics (e.g., gender) of interest
3. To assess the impact of at-home testing regimen on self-reported healthcare utilization for SARS CoV-2 treatment	Assessments: self-reported ED visits, hospitalizations, and ICU admission, for SARS CoV-2 evaluation or treatment	Point estimate and 95% confidence interval for each healthcare utilization measure and composite measure for the entire study cohort and stratified by participant demographics (e.g., gender) of interest
4. To assess knowledge of SARS CoV-2 prevention approaches over the study period	Assessments: self-reported data on perceptions and prevention of risks of contracting SARS CoV-2 infection	Proportion of respondents that are knowledgeable of precautionary measures to prevent infection for the entire study cohort and stratified by participant demographics (e.g., gender) of interest
5. Prevalence of positive test result for SARS CoV-2	Assessments: reported results of self-administered SARS CoV-2 antigen test	Prevalence of positive test results with 95% confidence intervals for the entire study cohort and stratified by participant demographic variables of interest

Exploratory		

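### The first secondary objective asks for change around a test result, but the endpoint and analysis named for it give only an after-result level

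*Combined protocol and SAP*

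**What the plan says.** Section 9.4.3, first bullet, gives the objective as to "assess change in self-reported behaviors before and following SARS CoV-2 at-home test result over the study period". Sections 1.1 and 3 carry the same objective.

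The measure in section 9.4.3 is staged: the objective is "measured via Precaution Adoption Process Model Assessments of self-reported data on awareness of the issue, engagement, decisions to act, action, and maintenance". The analysis that follows is: "The proportion of respondents that decide to act on precautionary behaviors after a test result will be analyzed for the entire study cohort", with strata by demographics. The endpoint in section 3 matches that analysis: "Proportion of respondents that decide to act on precautionary behaviors after a test result for the entire study cohort". The synopsis endpoint is the same, without the strata.

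Section 9.4.1 adds three general items: "Trends over time will be evaluated graphically"; "Stratified analyses by test or week number will also be performed"; and "We will explore the associations between positive test results and critical behavioral measures using mixed modeling techniques", with participant and household correlation taken into account. Section 9 opens with: "Additional details of the planned statistical analyses will be provided in a separate statistical analysis plan".

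Surveys fall at baseline and weeks 1, 3, 5, 13 and 21 (summary of changes; schedule in section 1.3).

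**The concern.** The objective needs two values per person, one before a result and one after. The endpoint and analysis use only the second. An analyst who follows section 9.4.3 exactly reports a level and cannot say whether behavior rose, stayed the same or fell.

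The staged measure adds a second difficulty. Deciding, acting and maintaining are listed as separate stages, and the text does not say whether the endpoint counts the deciding stage alone or that stage and any later one. Under the first reading, a person who moves from deciding to acting leaves the numerator. If both choices stay open until the data are seen, the direction of the reported result may depend on which reading is taken.

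**Working it through.** **1. Passages side by side.**

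| Element | Where | Before value? | After value? | Contrast? |
|---|---|---|---|---|
| Objective | 1.1, 3, 9.4.3 | yes | yes | yes (change) |
| Endpoint | 1.1, 3 | no | yes | no |
| Stated analysis | 9.4.3 | no | yes | no |
| Trends, strata by test or week | 9.4.1 | not stated | not stated | indexed to time or test number, not to a person's own result |
| Mixed models | 9.4.1 | no pre-result term stated | not stated | association with a positive result, exploratory |

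**2. A level does not fix a change.** The documents give no pre-result level, so these are assumed values. Change = after - before. With 80% after:
- 60% before: 80 - 60 = +20 points
- 80% before: 80 - 80 = 0
- 90% before: 80 - 90 = -10 points

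**3. The stage rule can reverse the sign.** Assume stages of 30/40/30% before (earlier / decided / acting or maintaining) and 20/30/50% after. One set of moves that gives this, in % of all participants: earlier to earlier 20, to decided 8, to acting 2; decided to decided 22, to acting 18; acting to acting 30. So 8 + 2 + 18 = 28% move forward and nobody moves back.
- Deciding stage alone: 30 - 40 = -10 points
- Deciding or later: (30 + 50) - (40 + 30) = 80 - 70 = +10 points

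**4. Precision of a change.** Section 9.2 sizes single proportions only. For N = 1,000 at 50% it gives 3.1% in the text and 3.09% in the table. Reproduced: 1.96 × sqrt(0.25/1000) = 3.10 points.

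For a paired change with 50% before and after and within-person correlation r, the margin is 1.96 × sqrt(2 × 0.25 × (1 - r)/n). The values of r, the 70% and the positivity rates are assumptions; 1% and 10% are illustrative proportions from section 9.2, applied here to 5,000 people.

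| Paired n | r = 0.3 | r = 0.5 | r = 0.7 |
|---|---|---|---|
| 1,000 (no loss) | 3.67 | 3.10 | 2.40 |
| 700 (70% usable) | 4.38 | 3.70 | 2.87 |
| 500 positives (10% of 5,000) | 5.19 | 4.38 | 3.39 |
| 50 positives (1% of 5,000) | 16.40 | 13.86 | 10.74 |

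These margins ignore household clustering, which would be expected to widen them.

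Break-even with the after-only margin when a fraction f has a usable pre-result survey: 2(1 - r)/f = 1, so r = 1 - f/2. This gives r = 0.50 for f = 1 and r = 0.65 for f = 0.7. Below these values the change is less precise than the level.

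**The case against.** The strongest reply is that the plan may deliver the change by another route. Section 9.4.1 has time trends, strata by test or week, and mixed models that allow for participant correlation. With repeated surveys these could yield before-and-after information, and section 9 promises a separate plan. This stands in part. A reader might infer that the study will not analyze change at all, but the documents do not support that. They show only that no before-to-after contrast is stated for this objective in the supplied text. The promise of further detail does not remove the mismatch, because it lies in the endpoint itself.

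Second, deciding to act after a result could be read as a decision newly made after it, hence a transition. But the endpoint requires no earlier stage, so a person who had decided before the result counts equally.

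Third, this is a secondary objective in a study that sections 9.1 and 9.4.1 call primarily descriptive, with no power calculation. That lowers the stakes, but a descriptive study can still describe a change, and this objective says that it will.

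Finally, a reader might extend the criticism to the primary comparison. The documents do not support that: the primary objective concerns interactions following a result, and its after-result endpoint matches.

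**Conclusion.** The point holds for the supplied text. Objective 2 asks for a change, and every endpoint and analysis named for it is an after-result level. That mismatch is certain. Whether a change will be analyzed under the separate plan is unknown.

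The size cannot be fixed from the documents, which give no pre-result level, stage distribution, within-person correlation or positivity rate. The illustrations show that the sign is undetermined (+20 to -10 points for one after-result figure) and that the unstated stage rule can turn +10 into -10. They show what is possible, not what is likely. The consequence is moderate: a stated secondary objective goes unanswered if section 9.4.3 is followed as written. It should be settled before analysis.

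**What to change.** In sections 1.1, 3 and 9.4.3, add for objective 2 the within-person change in the proportion at the deciding stage or any later stage, from the last survey before the index result to the first survey after it. Report it with a 95% confidence interval, overall and by positive or negative result, together with a stage-transition table. State the index-result rule in advance. The first reported positive is one option; participants with only negative results would need one prespecified survey interval. Report how many participants have no usable pre-result survey. If only the after-result level is intended, reword objective 2 to cover behavior following a result, and state which stages count.

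The cost is wording and modest programming, with no new survey proposed. Two items must be confirmed:
- **Test dates.** Section 6.4 describes a test-history tracker and section 10.1.9.1 an audit trail of data entry, but neither says that the test date is stored.
- **Behavior items at baseline.** The behaviors row in section 1.3 has no marks of its own in the extracted text. This is probably a merged cell.

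Downsides: participants without a pre-result survey leave the paired analysis. Kits arrive before the sub-study is offered (section 4.1), so even the baseline survey may follow a first test. The change is less precise than the level below the break-even correlations shown above, and it is imprecise in positives if positivity is low.

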Rapid Acceleration for Diagnostics in Underserved Populations:
HOME TESTING
(RADx-UP HoT)

National Clinical Trial (NCT) Identified Number: Pending

Principal Investigators: [name] PhD MPH

Co-Investigators: [name], MSc

[name], DrPH, MPH

Sponsor: National Institute of Health

Funded by: National Institute of Health

Version Number: 2.0

19 May 2021

NCT04949243

Summary of Changes from Previous Version:

Affected Section(s)	Summary of Revisions Made	Rationale
Sections 1.1, 1.3, 4.1, 4.4, and 9.3	The at-home testing through the public health intervention will be 3 times a week for 4 weeks, instead of testing twice a week for 5 weeks.	More frequent testing is better suited to diagnosing asymptomatic/pre-symptomatic disease and prevent spread.
Section 1.3	Questionnaires/surveys will be administered only on baseline and weeks 1, 3, 5, 13, and 21. The Schedule of Events table has been updated to reflect these timepoints.	To reduce participant burden, questionnaires/surveys will only be administered on baseline and weeks, 1, 3, 5, 13, 21.
Section 1.3	The survey on knowledge of prevention approaches will be administered on weeks 5 and 21 instead of weeks 13 and 21.	Administering this questionnaire at week 5 and week 21 allows for a better perspective to see how the participant's knowledge has changed over time.
Section 1.3	The survey on feasibility of at-home testing has been removed from week 21. It will only be administered at week 5.	To reduce participant burden, this survey will only be asked once after the testing phase.
Section 1.3	Survey questions on Beliefs were added to the protocol for weeks 1, 5, and 21.	No new questions were added. The survey questions on Belief were already included in the questionnaire. It has now been specified as a new category of questions within the protocol.
Section 1.3	Anthropometrics (weight) was added as a measure to be taken at Baseline and week 5. Anthropometrics (height) was added as a measure to be taken at Baseline.	Socio-Demographic Data was already planned at Screening and Enrollment (now called Baseline). For additional clarity, anthropometrics have now been specified at Baseline. Height will be taken at Baseline. Since weight fluctuates, it will be taken at Baseline and week 5.

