Study Population:	Adults and children > 8 years of age living within pre-identified communities participating in the public health intervention
Phase:	Not applicable

Description of Sites/Facilities Enrolling Participants:	This is a site-less, direct to participant study. Participants, up to 300,000, will be recruited for the sub-study within the communities participating in the larger public health intervention.
Description of Study Intervention:	Collection of survey data
Study Duration:	Total of up to 29 weeks, including up to 4 weeks of screening period and 25 weeks from the start of the study.
Participant Duration:	Up to 25 weeks: 4 weeks of active testing period and 17 weeks of follow-up. Last follow-up will be at week 21 with a 4 week window (up to week 25) to complete the surveys.

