7.2 PARTICIPANT DISCONTINUATION/WITHDRAWAL FROM THE STUDY

Participants are free to withdraw from participation in the study at any time. The reason for participant discontinuation or withdrawal from the study will be collected on the app or through phone call via call center. Participants who provide consent, and subsequently withdraw, will not be replaced.

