9.3 POPULATIONS FOR ANALYSES

The following populations are also defined:

Population	Description
Evaluable Population- Per protocol (PP)	Per protocol population will be those that report adhering to the following: 
 1. Self-administer the at-home test three times a week for 4 weeks 2. Complete questionnaires/surveys during the 4 week testing period
Modified per-protocol	Will include any participant who performed at least one at-home test
Second modified per-protocol	Will include any participant who completed at least one survey

All analyses will be conducted in the PP. A subset of analyses will be repeated in the modified PP populations as applicable.

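### A Week 5 to Week 21 difference in prevention knowledge may reflect who answered at Week 21, because the plan gives a proportion of respondents and no within-person change

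*Combined protocol and SAP*

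**What the plan says.** - **Objective.** Section 9.4.3 states: "The third secondary objective is to assess knowledge of SARS CoV-2 prevention approaches over the study period".
- **Timing.** The schedule of activities (1.3) places the knowledge survey at Weeks 5 and 21 only, with no Baseline measure. The summary of changes at the front of the protocol gives the reason: "Administering this questionnaire at week 5 and week 21 allows for a better perspective to see how the participant's knowledge has changed over time".
- **Analysis.** Section 9.4.3: "The proportion of respondents that are knowledgeable of precautionary measures to prevent infection will be analyzed for the entire study cohort". Section 9.4.1 adds: "Trends over time will be evaluated graphically". It also allows analyses stratified by week.
- **Analysis sets (9.3).** All analyses use the per-protocol set, whose survey condition is "Complete questionnaires/surveys during the 4 week testing period". The two modified sets need one test or one survey.
- **Follow-up.** The synopsis describes "4 weeks of active testing period and 17 weeks of follow-up". Section 4.4 defines completion on the testing weeks alone, says later surveys will still be offered, and accepts whatever responses arrive.
- **Further detail.** Section 9 defers additional analysis detail to a separate statistical analysis plan. The text supplied has no paired analysis of knowledge, no comparison of responders with non-responders and no missing-data method.

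**The concern.** The stated interest is how a participant's knowledge changes, which is a within-person question. The stated summary is a proportion whose denominator is whoever answered. Sixteen weeks separate the two knowledge surveys, participation is remote and voluntary, and no analysis set fixes who is in the denominator at Week 21. Read literally, the per-protocol set does not require a Week 5 answer either.

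If people who know more about prevention are also more likely to keep answering, a plot of the two proportions rises with nobody having learned anything. If they are less likely to answer, it falls. A reader of the third secondary objective could take either movement as a change in knowledge.

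Vaccine attitudes (third exploratory objective) are also summarised as a distribution over respondents and are open to the same problem where the items are repeated. The schedule has no row under that name, so the text does not show how often they are.

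**Working it through.** **1. The plan's own precision figures.** The table in 9.2 gives 95% margins for a single proportion. For N = 1,000 and 50%, 1.96 × √(0.5 × 0.5 / 1,000) = 3.10 points. Multiplying by √((300,000 − 1,000) / 299,999) gives 3.09, as printed. With this finite-population factor, using the 300,000 maximum enrolment, all 12 cells reproduce to two decimals; without it only 3 do. The factor is inferred, as the protocol does not state it. The table covers sampling error in one proportion, with every one of the N answering.

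**2. Inputs for the illustration.** The documents give no dropout rate and no expected level of knowledge, so all of these are assumptions:
- p = 60% knowledgeable at Week 5;
- no individual changes, so the true change is 0;
- r1 = 70% of the knowledgeable answer at Week 21;
- r0 = the share of the others who answer, varied.

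**3. Formula.** Apparent Week 21 proportion = p·r1 / (p·r1 + (1 − p)·r0).

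| r0 | Calculation | Week 21 proportion | Apparent change (points) |
|---|---|---|---|
| 70% | 0.42 / 0.70 | 60.0% | 0 |
| 65% | 0.42 / 0.68 | 61.8% | +1.8 |
| 60% | 0.42 / 0.66 | 63.6% | +3.6 |
| 50% | 0.42 / 0.62 | 67.7% | +7.7 |
| 40% | 0.42 / 0.58 | 72.4% | +12.4 |

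Reversing the selection (r1 = 60%, r0 = 70%) gives 0.36 / 0.64 = 56.3%, a fall of about 3.8 points.

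**4. Other starting levels.** With p = 50% and response 80% against 70%, 0.40 / 0.75 = 53.3%, or +3.3 points. With p = 80% and the same response rates, 0.64 / 0.78 = 82.1%, or +2.1 points.

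**5. Against sampling error.** Take the +3.6 case. Of 1,000 people answering at Week 5, 660 answer at Week 21. That wave's margin is 1.96 × √(0.636 × 0.364 / 660) = 3.67 points, so the shift lies within it. With 5,000 at Week 5 (3,300 at Week 21) the margin is 1.64 points, and with 10,000 (6,600) it is 1.16. The shift stays at 3.6 points whatever the sample size.

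**6. Within-person change in the same scenario.** With r0 = 50%, 620 of 1,000 answer both surveys. Of these, 420 were knowledgeable at Week 5 and the same 420 at Week 21. That is 67.7% at both waves, so the paired change is 0. The unpaired display goes from 60.0% of 1,000 to 67.7% of 620.

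**The case against.** The best defence is that the plan commits to no Week 5 versus Week 21 comparison. Section 9.1 calls the analysis mainly descriptive, and 9.4.3 names no test or estimate of change. That is correct: a reader might infer that the plan formally compares two different groups as one cohort, and the documents do not say so. What stands is that the knowledge survey was timed to show change, and the only summaries offered for it are respondent proportions and graphs. A descriptive trend can mislead too.

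A reader might also infer that distancing and behavior share the defect. The documents support this only in part. Section 9.4.1 specifies tests of proportions that allow for clustering within participant, and mixed models for behavioral measures. These use repeated answers from the same person, and a likelihood-based mixed model gives some protection if response depends only on observed data. The primary endpoint is a positive-versus-negative contrast after a test result, and scheduled testing ends at Week 4, so it is not the target here. Neither method is stated for knowledge.

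Retention is actively supported: payment of as much as $50 for finishing every survey (5.5), reminders through Week 21 (1.3), call-center contact (7.3) and a 4-week window for the last survey (1.1). These may well reduce non-response. They do not make it unrelated to knowledge.

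The rule in 7.2 that "Participants who provide consent, and subsequently withdraw, will not be replaced" adds nothing to the concern, since replacements could not supply a leaver's later answers. Finally, the separate analysis plan may settle the matter. Its content is not in the text supplied, so the point is also a request for what that plan should contain.

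**Conclusion.** The point holds for knowledge of prevention, and for vaccine-attitude items where they are repeated. As written, the plan cannot separate a change in knowledge from a change in who answered.

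The size cannot be fixed from the documents. Over the assumed range the artefact runs from 0 with equal response to +12.4 points with a 30-point gap in response, and it is negative if selection is reversed. It requires response at Week 21 to depend on knowledge. A reader might infer that attrition is bound to show up as a gain, but neither its presence nor its direction is established. Nor does every scenario exceed sampling error: with 1,000 participants at Week 5, a 10-point response gap produces a shift inside the Week 21 margin. With several thousand participants the same gap would look like a clear trend.

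**What to change.** In 9.4.1 and 9.4.3, or in the separate statistical analysis plan:

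1. Keep the proportion of respondents at each wave as the defined endpoint.
2. Base any statement of change in knowledge on the within-person change from Week 5 to Week 21, with a 95% confidence interval, in participants who answered both surveys. Do the same for vaccine-attitude items asked more than once.
3. Report the number responding at each wave, and set out the Baseline profile and Week 5 knowledge answer of Week 21 responders beside those of non-responders.
4. Optionally, add response-weighted proportions as a sensitivity analysis. Knowledge has no Baseline measure, so the weights for people who did not answer at Week 5 must omit the prior-answer term.

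The cost is analysis-plan wording and modest programming. All the data are already scheduled and no study procedure changes. The downside is that the paired set is smaller and describes only those who stayed, who may have changed differently from those who left; item 3 lets the reader judge how far that matters. Weighting, if used, relies on the measured variables explaining who responds, which is one reason to leave it as a sensitivity analysis.
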